#### PHASE 2: FIELD TRIAL

- 4.1.3 Phase II Field Trial. The purpose of the field trial will be twofold. The field trial will extend usability testing over time and under real life conditions. In addition, the field trial will be used to collect data to develop and evaluate machine learning methods. IntelliCare will be evaluated in up to 200 individuals meeting inclusion criteria in a 8-week, single arm field trial.
- Phase II Enrollment. Participants in the field-trial will be enrolled remotely to avoid excluding 4.1.3.1 participants with access barriers who are among those who would be likely end users. Interested parties will complete a brief telephone or web screen to determine whether there is any reasonable expectation that they might be eligible (data from the brief screen will be included in the study dataset). If they are clearly not eligible they will be informed of this and thanked. If they are eligible they will initiate the consent process. Following the initial pre-consent screening phone call but prior to the eligibility interview, the participant will be emailed a link to the detailed digital version of the consent form. Subjects agree to participate by checking a yes box and typing in their name. They are instructed to print out the consent form for their records. After the study consent form is signed online, detailed information regarding the consent will be reviewed with the participant and witnessing of the consent form will take place at this time by study staff. A date and time for the screening assessment will then be scheduled. An RA will then conduct an eligibility interview with the participant over the phone, where the MINI, HAM-A, and QIDs are administered. Questionnaires will be administered to patients via a secure web based assessment portal, so that the other inclusion and exclusion criteria can be determined. Patients will be paid \$20 for completing the eligibility interview. Payments may be made in either Amazon credits or by check depending on participant preference, NU payment policies, and payment availability at the time of study participation.

If eligible, a research study assistant will work with participants to download the IntelliCare system from the Google Play store. Eligible participants will include those who already own an Android smartphone with an operating system sophisticated enough to support the IntelliCare system (version 4.2.2 or higher).

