- Phase II Assessment, Measures & Compensation. Participants in the field trial will receive telephone-4.1.3.3 based interview evaluations and complete online self-report questionnaires at baseline, week 4 and week 8. All assessments and evaluations will be conducted by an RA who is blind to the treatment (i.e. coaches will not perform assessments on patients they coach). Depression will be measured at baseline by telephone interview using the QIDS-C for severity of symptoms and the MINI MDE module for diagnosis. Self-reported depression will be measured at baseline, wk4 & wk8 using the PHQ-9 administered online. Anxiety will be measured by telephone interview using the HAM-A for severity of symptoms at baseline. Self-reported anxiety will be measured using the GAD-7 administered online at baseline wk4, and wk8. Adherence will be assessed through use data from phone or other platforms (e.g. computer), including number of times the program was accessed, number of times each lesson, tool, and feedback element was accessed and percentage of messages viewed. The first 20 participants will also be engaged in extended usability testing, and will speak with a research assistant weekly, who will inquire into usability problems. We will compensate \$70 to each of the 200 field trial participants for taking part in their follow up assessments (Week 4 and Week 8). Participation in the trial may include the use of texting, and as such, study staff will reimburse participants who do not already have an unlimited monthly texting plan for their upgrade to such. Reimbursement of up to \$30 per month enrolled in the trial (up to two months) is possible. We will not be compensating participants who already subscribe to unlimited texting in their monthly plans. This decision was made in attempt to make the intervention more generalizable, so as not to overincentivize certain users by compensating them for matters already routine to them. Payments may be made in either Amazon credits or by check depending on participant preference. NU payment policies. and payment availability at the time of study participation.

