### **6** STATISTICAL CONSIDERATIONS

- **6.1** Public Deployment
- **6.2** Adherence Outcomes:
- 6.3 The primary outcome of Phase 1a will be rate of usage of each Intellicate application. This will be

examined by calculating standard descriptive statistics for the number of downloads and launches of each application. Secondary analyses of the primary outcome will include comparisons of co-usage of Intellicare application pairs, which we will test using Pearson correlations.

- **6.4** Field Trial
- **6.5** Power/sample size:
- 6.5.1 We estimate that we will have a 20% dropout, which will give us 80% power to detect effect sizes of 0.30. Power calculations were performed using Pass 2008.(Hintze, 2008)
- **6.6** Adherence Outcomes:
- 6.6.1 The primary outcome will be time to last use of a treatment element (lesson or tool), and will be tested between groups using traditional survival (Kaplan-Meier) methods, where the event of interest is last use from intervention start. Secondary analyses of the primary outcome would include Cox regression models that would adjust for potential effect modifiers or moderators such as gender, race, and age.
- **6.7** Patient Centered Outcomes:
- 6.7.1 Although power was presented for independent t-tests, primary analyses for patient centered outcomes (PHQ-9 and GAD-7) will utilize dependent t-tests
- **6.8** Mediation Analyses:
- 6.8.1 Mediators, such as app usage, we be examined in mediation models as time-varying covariates. We used the framework of Muller and colleagues(Muller, Judd, & Yzerbyt, 2005) to identify those variables, which mediate the effects of treatment on depression and anxiety. Only if the 4 criteria specified by Muller are satisfied (treatment effect for depression, treatment effect for the mediator, effect of mediator on depression, and reduction of treatment effect when mediator is included), will we calculate the effect of mediation using MacKinnon and colleagues' product of coefficients method.(MacKinnon, Lockwood, Hoffman, West, & Sheets, 2002) Bias-corrected 95% confidence intervals for the mediated effect will be calculated using bootstrapping.(Shrout & Bolger, 2002)
- 6.8.2 Development of the recommendation engine algorithms will use machine learning and Baysean. statistical methods that will continuously learn that will continuously learn from user interactions with IntelliCare to provide intervention recommendations.
- **6.9** Randomized Control Trial
- **6.9.1** Power/sample size:

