#### **6.10** Adherence Outcomes:

- 6.10.1 The primary outcome will be time to last use of a treatment element (lesson or tool), and will be tested between groups using traditional survival (Kaplan-Meier) methods, where the event of interest is last use from intervention start. Secondary analyses of the primary outcome would include Cox regression models that would adjust for potential effect modifiers or moderators such as gender, race, and age.
- **6.11** Patient Centered Outcomes:
- 6.11.1 Although power was presented for independent t-tests, primary analyses for patient centered outcomes (QIDS-C, MDD, and PHQ-9) will utilize generalized linear mixed (GLM) models (with link functions depending on the distribution of the outcome), that can examine patterns over the course of treatment and follow-up, and can account for missing data.(Gibbons et al., 1993)
- **6.12** Secondary Mediation Analyses:
- 6.12.1 Mediators will be entered into our models as time-varying covariates. We used the framework of Muller and colleagues(Muller, Judd, & Yzerbyt, 2005) to identify those variables, which mediate the effects of treatment on depression. Only if the 4 criteria specified by Muller are satisfied (treatment effect for depression, treatment effect for the mediator, effect of mediator on depression, and reduction of treatment effect when mediator is included), will we calculate the effect of mediation using MacKinnon and colleagues' product of coefficients method.(MacKinnon, Lockwood, Hoffman, West, & Sheets, 2002) Bias-corrected 95% confidence intervals for the mediated effect will be calculated using bootstrapping.(Shrout & Bolger, 2002)
- 6.12.2 Development of the recommendation engine algorithms will use machine learning and Baysean. statistical methods that will continuously learn that will continuously learn from user interactions with IntelliCare to provide intervention recommendations.
- **6.12.3** Exploration of moderating variables on outcomes, such as baseline demographics, baseline characteristics.
- 2.2.3 Explore, optimize, and validate coaching methods. This will include analyses of all data captured in the delivery of coaching, including the timing and content of messages and phone calls, and coach records related to participant encounters.

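### The field trial's paired t-tests on PHQ-9 and GAD-7 use completers only and overstate improvement if poor responders leave; a three-visit mixed model would be the better primary analysis

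*Combined protocol and SAP*

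**What the plan says.** The field trial is uncontrolled: "IntelliCare will be evaluated in up to 200 individuals meeting inclusion criteria in a 8-week, single arm field trial" (4.1.3).

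Both scales have three scheduled visits (4.1.3.3). For depression: "Self-reported depression will be measured at baseline, wk4 & wk8 using the PHQ-9 administered online". For anxiety: "Self-reported anxiety will be measured using the GAD-7 administered online at baseline wk4, and wk8".

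The analysis is given in one sentence in 6.7.1: "primary analyses for patient centered outcomes (PHQ-9 and GAD-7) will utilize dependent t-tests". It does not name the visits to be compared. Nothing in the field-trial part of section 6 gives an imputation rule, a repeated-measures model or a missing-data sensitivity analysis for these outcomes.

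On losses, 6.5.1 says: "We estimate that we will have a 20% dropout". The term is not defined there. Section 4.4.1 allows follow-up to continue after a participant voluntarily withdraws from treatment.

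For the randomized trial, 6.11.1 chooses mixed models for QIDS-C, MDD and PHQ-9, partly because they examine the course over time "and can account for missing data". GAD-7 is not on that list.

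**The concern.** A paired t-test works on within-person differences, so a person without the second score contributes nothing. The estimate is the mean change among completers. It equals the mean change among all enrolled only if those who leave would have changed by the same amount on average.

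The plan gives two reasons to doubt that. Section 6.9.2 links three more weeks of participation to an 11% improvement in depression severity. Section 4.4.4 can end follow-up, not only treatment, on disease progression. Both point towards losing people who are doing less well.

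In a single-arm study no comparison group shares the distortion, so any completer bias goes straight into the reported pre-post improvement. The scheduled week-4 scores carry information about people who later go missing, and a baseline-to-week-8 paired test cannot use it.

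**Working it through.** **Inputs from the plan.** N up to 200 (4.1.3); dropout 20% (6.5.1); visits at baseline, week 4 and week 8 (4.1.3.3); dependent t-tests (6.7.1). If dropout is read as a missing week-8 score, 0.20 × 200 = 40 people are excluded and 160 remain.

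**The plan's own figure.** Section 6.5.1 states: "We estimate that we will have a 20% dropout, which will give us 80% power to detect effect sizes of 0.30". With two-sided 5% assumed (no alpha is stated for the field trial), a paired t-test on 160 completers has 96.5% power at a standardized change of 0.30 and 80% power at 0.223. An independent t-test gives 76.3% with 160 per occasion, or 47.1% with 160 split 80/80. None of these is the stated 80%. That mismatch is a separate matter. Here it shows only that precision is ample for a paired test, so the issue is bias.

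**Bias without a model.** Let m be the share missing week 8, C the mean improvement in completers, and f × C the mean improvement in those missing.

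- Mean over all enrolled = (1 − m)C + m f C.
- Relative overstatement by completers = 1 / (1 − m + m f) − 1.

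| f (dropouts relative to completers) | m = 0.20 | m = 0.10 |
|---|---|---|
| 1.25 | 1/1.05 − 1 = −4.8% | 1/1.025 − 1 = −2.4% |
| 1.00 | 0% | 0% |
| 0.75 | 1/0.95 − 1 = 5.3% | 1/0.975 − 1 = 2.6% |
| 0.50 | 1/0.90 − 1 = 11.1% | 1/0.95 − 1 = 5.3% |
| 0 | 1/0.80 − 1 = 25.0% | 1/0.90 − 1 = 11.1% |

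The m = 0.10 column is an assumption, showing what happens if half of those counted as dropouts still give a week-8 score.

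**What using week 4 would recover.** This was checked by large-sample simulation. All inputs are assumptions, since the documents give none:

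- true change 0.80 SD;
- correlations 0.6 (baseline to week 4), 0.7 (week 4 to week 8) and 0.5 (baseline to week 8);
- 20% missing at week 8, with the log-odds of being missing rising by 0.5 to 2.0 per SD less improvement.

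The model column is a likelihood-type estimate that predicts week 8 from the earlier scores.

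| Dropout depends on | Week 4 available | Completers (SD) | Model (SD) |
|---|---|---|---|
| week-4 change | for everyone | 0.86 to 0.97 | 0.80 |
| week-4 change | for half of those missing week 8 | 0.86 to 0.97 | 0.82 to 0.85 |
| week-4 change | for none of those missing week 8 | 0.86 to 0.97 | 0.84 to 0.92 |
| unseen week-8 change | for everyone | 0.90 to 1.06 | 0.85 to 0.95 |

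In the first row completers overstate by 0.86/0.80 − 1 = 7% to 0.97/0.80 − 1 = 21%, and the model is unbiased. That is guaranteed by the set-up, because dropout there depends only on a score the model sees. In the last row the model still overstates by 0.85/0.80 − 1 = 6% to 0.95/0.80 − 1 = 19%, less than completers but not zero.

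**The case against.** The strongest case against is that this is an uncontrolled development phase. Section 4.1.3 gives its purposes as extended usability testing and collecting data for machine learning. Its primary outcome is time to last use (6.6.1). The pre-post change is not a treatment effect under either method, and no decision rule or sample-size input for the randomized trial uses it. All of that stands, and it limits the consequence. It does not remove the point, because 6.7.1 itself calls this the primary analysis of the patient-centered outcomes.

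Four stronger readings are tempting, and the documents do not support them:

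- **That week 4 is ignored.** The visits are unnamed and the tests are plural, so a separate baseline-to-week-4 test may be intended. What holds is that a paired test cannot use week 4 to inform a missing week-8 score.
- **That 20% will certainly be excluded.** The only definition of dropping out, in 6.9.2, concerns stopping participation in the intervention. Follow-up may continue after treatment withdrawal (4.4.1), and the follow-up assessments are paid (4.1.3.3). The share missing week 8 could be smaller, and the bias shrinks with it.
- **That the plan already applies a mixed model to both scales.** Section 6.11.1 lists PHQ-9 but not GAD-7, and the randomized trial has five visits rather than three.
- **That the mixed model cures the problem.** It does so only if dropout depends on recorded scores. Week 4 is scheduled for everyone, but those lost early may not have it.

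**Conclusion.** The point holds as a recommended change of primary method, not as a fault that invalidates the trial. With 20% missing at week 8, the completer mean overstates improvement by about 11% if dropouts improve half as much as completers and by 25% if they do not improve at all. The direction depends on who leaves: the bias is zero if dropouts improve equally and turns into understatement (−4.8%) if they improve 25% more. The plan's own statements make loss of poor responders plausible but do not establish it.

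The size rests on reading dropout as a missing week-8 score and on an assumed gap between completers and dropouts, for which the documents give no figure. A reader might infer that a headline efficacy result to be reported ahead of the randomized trial is at risk; the documents assign the field-trial change no such role. The randomized trial's mixed-model analysis and the field trial's primary adherence outcome are not affected.

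**What to change.** In 6.7.1:

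1. Make the primary analysis of PHQ-9 and GAD-7 a repeated-measures mixed model on baseline, week 4 and week 8 for all enrolled participants, with visit as a category and an unstructured covariance. Report the week-8 minus baseline mean with its 95% interval.
2. Keep the paired t-test, with its visits named, as a completer sensitivity analysis.
3. Add a sensitivity analysis that assumes less improvement in those missing week 8 than the model predicts, over a stated range. With 20% missing, each 0.1 SD of assumed shortfall lowers the overall estimate by 0.2 × 0.1 = 0.02 SD, so the effect is easy to report.
4. State whether the 20% in 6.5.1 means stopping the intervention or lacking a week-8 score, and report how many have each visit.

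The cost is a few sentences of plan text and a little more analysis work. No new data are needed. If loss is unrelated to response, the model and the paired test should broadly agree and the report can show it.

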#### 2 STUDY OBJECTIVES

- **2.1** Primary Objectives
- 2.1.1 Develop IntelliCare and optimize its functionality through laboratory and field usability testing.
- 2.1.2 Develop the machine learning models and algorithms that will continuously learn from user interactions with IntelliCare to provide intervention recommendations and motivational messaging.
- 2.1.3 Conduct a randomized controlled trial (RCT) comparing 8 weeks of IntelliCare with the machine learning component to 8 weeks of IntelliCare without the machine learning component for the treatment of depression and anxiety. Participants will be evaluated at baseline, week 4, week 8, and at 3- and 6-month post-treatment follow-ups. It is hypothesized that 1) IntelliCare with the recommendations, in contrast to IntelliCare without the recommendations, will produce greater adherence and greater reductions in depressive and anxiety symptoms and 2) IntelliCare with coaching will produce greater greater adherence and greater reductions in depressive and anxiety symptoms. The primary patient centered outcome will be depression/anxiety severity.
- 2.2 Secondary Objectives.
- 2.2.1 Exploration of the mediating effects of adherence markers (e.g. time in treatment, app launches, etc.) coaching variables (e.g. message frequency, timing, etc.), and psychological variables (e.g. change in self-report measures) on depression and anxiety outcomes.
- **2.2.2** Exploration of moderating variables on outcomes, such as baseline demographics, baseline characteristics.
- 2.2.3 Explore, optimize, and validate coaching methods.

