# PHASE 3 RANDOMIZED CONTROLLED TRIAL

- 4.1.4 Phase III Randomized Controlled Trial. For the RCT, 300 participants meeting entry criteria will be enrolled over 13 months (approximately 23 per month). Participants will be randomized using a factorial design with the following factors:
- **4.1.4.1** Factor 1. Hub App with intelligent recommender system/Hub app without intelligent recommender system: This factor is consistent with Objective 2.1.3 on pg. 4
- **4.1.4.2** Factor 2. Coaching/No Coaching: This factor would allow us to examine and control for the effect of coaching.
- **4.1.5** *Phase III Enrollment.* Participants in the RCT will be enrolled remotely to avoid excluding individuals with access barriers who are among those who would be likely end users. Screening will be conducted in 3 stages.
- 4.1.5.1 Screening Stage 1 (pre-consent): Interested parties will complete a brief web screen to determine whether there is any reasonable expectation that they might be eligible (data from the brief screen will be included in the study dataset). If they are clearly not eligible they will be informed of this and thanked. If they appear to be eligible a research assistant will follow-up by phone to clarify responses from the web screen and ask additional phone screening questions. If the participant passes the stage 1 phone screen s/he will be invited to initiate the online consent process and proceed to screening stage 2 described below.

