- **4.1.5.4** Study Enrollment: A research study assistant will work with participants to download the IntelliCare apps from the Google Play store, and if assigned to work with a coach, schedule the coach orientation call.
- **4.1.6** *Phase III Treatment Plan.* The IntelliCare intervention will be comprised of a combination of 3 components: (1) IntelliCare Treatment Apps, (2) IntelliCare Hub App, (3) and Coaching. A brief description of each component appears below.
  - 1. IntelliCare Treatment apps: There are 13 IntelliCare treatment apps. Each app instantiates a single behavioral strategy (e.g. scheduling positive behaviors, thought restructuring, goal setting, etc.), and takes only a few seconds to use. The apps address specific treatment goals, and may include didactic content as well as interactional components (e.g. activity scheduling/monitoring, thought records, etc.) that support behavior change. All participants will download the apps onto their own phones and use them daily during the 8 week intervention period.
  - 2. IntelliCare Hub app: The "Hub" app integrates the treatment apps and organizes the user's experience. We will be testing two different versions of the hub app; one with an intelligent recommender system (version A) and one without (version B). The recommender system in version A will use machine learning, which can learn from a patient's interactions with the intervention, to deliver and adapt treatment to the needs and preferences of the participant.
  - 3. Coaching: BA level coaches (supervised by a licensed psychologist), may support participants throughout the 8 week intervention period. We have developed a low-intensity coaching model that relies primarily on brief text messaging to promote engagement, along with one engagement orientation call at the beginning of treatment, and the option of a second call if needed.

While **all** participants will have access to the treatment apps during the 8-week intervention period, the version of the Hub app and the inclusion of coaching will vary for each participant according to random assignment to one of 4 groups:

```
Group 1 (n=75): Hub App Version A + Treatment Apps + Coaching
```

Group 2 (n=75): Hub App Version A + Treatment Apps + Independent Use (no coaching)

Group 3 (n=75): Hub App Version B + Treatment Apps + Coaching

Group 4 (n=75): Hub App Version B + Treatment Apps + Independent Use (no coaching)

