At the end of the 8 week intervention, all participants will be informed that they may continue using the IntelliCare system on their phones but participants in groups 1 and 3 will no longer have access to their coach. For any participants who do continue app use after the study period has ended, the IntelliCare system will continue to collect app data as before.

4.1.6.1 Phase III Assessment, measures and compensation. RCT participants will receive trial assessments at baseline, week 4, and week 8 (post-treatment). Post-treatment follow-up evaluations will occur at 3 and 6 months to evaluate maintenance of gains. Assessments will consist of telephone based interviews and online self-report questionnaires. All assessments and evaluations will be conducted by an RA (i.e. coaches will not perform assessments on patients they coach). Depression will be measured at baseline by telephone interview using the MINI MDE module. Self-reported depression will be measured at baseline, wk4, wk8, 3 months post-treatment and 6 months post-treatment using the PHQ-9 administered online. Self-reported anxiety will be measured using the GAD-7 administered online at

baseline wk4, wk8, 3 months post-treatment and 6 months post-treatment. *Adherence* will be assessed through app use data from phone, including number of times the apps were accessed, number of times each app feature was accessed and percentage of messages viewed. Participants will be paid up to \$40 for the screening/baseline assessments, \$30 for the week 4 and 8 assessments, and \$30 for the 3 and 6 month assessments (total= up to \$160). Participants will not be compensated for using the apps or communicating with the study coach. Payments may be made in either Amazon credits or by check depending on participant preference, NU payment policies, and payment availability at the time of study participation. Individuals recruited through Focus Pointe Global will be paid through PayPal by Focus Pointe Global.

**4.1.7** *Phase II Study Retention.* Communication from the research study may occur across a participant's involvement in the trial to increase participant retention. Such contact could include sending greeting cards via mail or email (thank you, birthday, etc.) or sending small tokens of appreciation (keychains, pens, stress balls).

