#### 4.3 Data

- **4.3.1.1.1** *Adherence:* The primary adherence outcome will be length of time from initiating treatment to last use of treatment elements. We will also explore the motivational system by examining the number of motivational messages delivered, number viewed and the ratio of viewed/delivered by treatment arm. More specifically:
- **4.3.1.1.1.1** Messages include text and email messages between participants and study staff for the purposes of coaching and participant management.
- **4.3.1.1.2** App use includes the number, timing, and duration, application launches and launches of specific pages within the app.

- **4.3.1.1.2** *Depression:* Primary patient centered outcomes will use continuous measures of depression and anxiety.
- **4.3.1.1.2.1** *PHQ-9* will be used to evaluate self-reported depression. GAD-7 will be used to evaluate self-reported anxiety.
- **4.3.1.1.3** *Secondary Outcome Measures* will include the following (for a full list of self-report measures see Measures Appendix):
- **4.3.1.1.3.1** *Satisfaction*, measured using the USE questionnaire, which was designed to measure satisfaction, usefulness, ease of use, and ease of learning.

*Moderators and mediators* will include the measures provided prior to initiating treatment the Mini International Neuropsychiatric Interview, the SCT Motivation assessment, Behavioral Activation, wellbeing and quality of life, Coping, and

**4.3.1.1.3.2** Audiofiles include audio recordings of coaching and assessments. Audio files may be transcribed by one or more of the following NU transcription vendors:

GMR Transcription https://www.gmrtranscription.com/

Wordsworth https://wordsworthcoop.com

Files may be shared via secure access to FSM servers or through vendors' proprietary web-based applications for secure file management.

- **4.3.1.1.4** Coach generated notes on participant encounters.
- 4.4 Removal of Subjects from Study

Patients can be taken off the study treatment and/or study at any time at their own request, or they may be withdrawn at the discretion of the investigator for safety, behavioral or administrative reasons. The reason(s) for discontinuation will be documented and may include:

- 4.4.1 Patient voluntarily withdraws from treatment (follow-up permitted);
- 4.4.2 Patient withdraws consent (termination of treatment and follow-up);
- 4.4.3 Patient is unable to comply with protocol requirements; (termination of treatment and follow-up);

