- 6.9.2 Preliminary data indicates that approximately 50% of patients stop participating in BITs (which we define here as "drop out") by week 7 (see Sec. D.1.1). A sample size of 135/arm (total sample of 270) will provide 80% power to detect a difference in median drop out time from 7 to 10 weeks. We estimate from existing data (Sec D.1.1) that a 3 week increase would result in an 11% improvement in depression severity (ES=0.30). Additionally, this sample provides 80% power to detect an increase in continued participation from 50% to 61.6% at week 7. Both analyses are based on a log-rank test at a type 1 error rate of 5%, with accrual of 54 weeks and 12 weeks of intervention. Power for continuous patient

centered outcomes were based on independent t-tests, and would have 80% power to detect effect sizes of 0.34. Power calculations were performed using Pass 2008.(Hintze, 2008)

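### The 80% log-rank power for the adherence outcome uses a 12-week intervention in an 8-week trial and no stated censoring time; at N=300 power is about 58% at week 8 and about 80-85% with later horizons

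*Combined protocol and SAP*

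**What the plan says.** Section 6.9.2 (Randomized Control Trial, Power/sample size) says that 135 per arm, 270 in total, "will provide 80% power to detect a difference in median drop out time from 7 to 10 weeks". It adds that the same sample has 80% power for a rise in continued participation at week 7 from 50% to 61.6%. Both statements use a log-rank test at 5%, "with accrual of 54 weeks and 12 weeks of intervention".

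The trial is described differently elsewhere:

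- **Duration.** Objective 2.1.3 describes a trial "comparing 8 weeks of IntelliCare with the machine learning component to 8 weeks of IntelliCare without the machine learning component". In section 4.1.6 participants download the apps and "use them daily during the 8 week intervention period".
- **Size.** Section 4.1.4 says that "300 participants meeting entry criteria will be enrolled over 13 months". Section 4.1.6 divides them into four groups of 75.
- **Endpoint.** Section 4.3 defines the primary adherence outcome as "length of time from initiating treatment to last use of treatment elements". Section 6.10.1 and the Study Summary call time to last use the primary outcome and test it by Kaplan-Meier methods. None of the three gives a censoring time.
- **After week 8.** The end of section 4.1.6 says that for people who carry on, "the IntelliCare system will continue to collect app data as before", but it places that use after the end of the study period. It also says that "participants in groups 1 and 3 will no longer have access to their coach".

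**The concern.** Log-rank power depends on the number of events, and the number of events depends on how long each person is observed. The power paragraph uses an intervention length that the trial does not have. The endpoint definition leaves the observation window open. Section 4.1.6 can be read as ending observation at week 8 or as continuing it.

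Two things are at stake. First, this is the only power statement for the outcome that the Study Summary and section 6.10.1 call primary. If the adherence comparison is null, a reader cannot tell whether the test had about 58% or about 85% power. Second, an open horizon allows the cutoff to be chosen after the data have been seen.

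**Working it through.** **Inputs.** Medians of 7 and 10 weeks, 5% type 1 error, N=270, 54 weeks of accrual and 12 weeks of intervention (section 6.9.2); 8 weeks (2.1.3, 4.1.6); N=300 (4.1.4). Follow-up at 3 and 6 months post-treatment (4.1.6.1) is taken as 8+13 = 21 and 8+26 = 34 weeks from start.

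**Assumptions.** Exponential times, two-sided test, one factor compared at its margin with equal arms (150 versus 150 at N=300), no interaction and no loss of app data.

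**Effect size.** HR = 7/10 = 0.70. The week-7 claim is the same effect: 0.5^0.7 = 0.616.

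**Events needed for 80% power.** 4(1.96 + 0.8416)² / (ln 0.70)² = 246.8.

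**Reproducing the plan's figure.** Suppose accrual is uniform over R weeks and last use is followed until F weeks after accrual closes. With λ = ln 2 / median, P(event) = 1 − (e^(−λF) − e^(−λ(F+R))) / (λR). With R=54 and F=12, so 12 to 66 weeks per person, the probabilities are 0.943 and 0.886. Then 135 × (0.943 + 0.886) gives 247.0 events and 80.0% power, an almost exact match. Censoring each person at exactly 12 weeks gives 170.1 events and only 64% at N=270, so the plan's figure does not come from that reading.

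**Changing only 12 to 8 weeks.** With R=54 and F=8 the probabilities are 0.916 and 0.850. At N=270 this gives 238.4 events and 78.6%, a loss of 80.0 − 78.6 = 1.4 points. With 13 months of accrual (R=56.3) it is 78.8%.

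**Fixed horizon W.** P(event) = 1 − 0.5^(W/median), and power = Φ(|ln 0.70| × √events / 2 − 1.96). For W=8 the probabilities are 0.547 and 0.426. At N=300 that is 150 × 0.973 = 145.9 events, and Φ(2.154 − 1.96) = 57.7%.

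| Last use censored at | Events, N=270 | Power, N=270 | Events, N=300 | Power, N=300 |
|---|---|---|---|---|
| Week 8 | 131.3 | 53.3% | 145.9 | 57.7% |
| Week 12 | 170.1 | 64.3% | 189.0 | 68.9% |
| Week 21 | 221.6 | 75.6% | 246.3 | 79.9% |
| Week 34 | 252.6 | 80.9% | 280.6 | 84.8% |
| Study close, 54+8 weeks | 238.4 | 78.6% | 264.9 | 82.7% |

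Log-rank simulation (8000 runs) agrees for N=270 / N=300: 53.2% / 56.9% at week 8, 75.5% / 79.8% at week 21 and 80.9% / 84.9% at week 34.

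**If the effect ends at week 8.** Every row beyond week 8 assumes that HR 0.70 continues. In the limiting case of equal hazards after week 8 (both arms at the 7-week-median hazard), simulated power at N=300 is about 36% at week 21 and 34% at week 34. Later events then dilute the difference.

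**Detectable difference with a week-8 horizon.** 80% power needs medians of 7 versus about 11.5 weeks at N=270 (HR 0.606; 50% versus 65.7% still participating at week 7), or 7 versus about 11.2 weeks at N=300 (HR 0.623; 50% versus 64.9%). With week-8 censoring, 0.5^0.8 = 57% of the better arm would still be using under the plan's own alternative, so its 10-week median would not be observed.

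**The case against.** The best defence is that nothing was miscalculated. The 80% reproduces on a sensible model, and the 12-week input alone is nearly harmless: on that model the real design, with 8 weeks and 300 participants, has 82.7%. The endpoint definition has no upper limit and app data are collected after week 8, so a late horizon may be what was intended. On that view 58% is a lower scenario and not the trial's power. The case with no effect after week 8 is also extreme. It is motivated by the end of coaching and says little about the recommender factor, since participants may keep using the system. Finally, objective 2.1.3 makes depression/anxiety severity the primary patient-centred outcome, and its power statement (effect size 0.34) does not use the 12-week input.

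Much of this stands. The 58% is conditional, and the 34-36% is a bound relevant mainly to coaching. But the defence needs a follow-up model that is only inferred from a numerical match, and section 4.1.6 places later use outside the study period. A literal 12-week cutoff would not give 80% either. The extra 30 participants bring week 21 to 80% only if all 300 supply usable data; the plan does not say whether they are an allowance for loss.

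**Conclusion.** The concern holds. The 80% describes a design that is not the one planned and depends on a follow-up horizon that the plan does not define. The 12-versus-8-week discrepancy costs 1.4 points by itself; the missing censoring time makes the real difference. For medians of 7 versus 10 weeks, power at N=300 is about 58% with week-8 censoring and about 80% to 85% with horizons from week 21 to week 34 or study close. The like-for-like range at N=270 is 53% to 81%. These figures rest on the assumptions listed above and, beyond week 8, on a hazard ratio that stays at 0.70. That is least secure for the coaching factor. The week-7 participation claim carries the same conditions. Because a primary endpoint and its only power claim are affected, this must be corrected.

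**What to change.** 1. In section 6.10.1, and to match in 4.3, state the time at which participants still using the apps are censored: week 8, month 3, month 6 or study close.
2. In section 6.9.2, replace the 12-week input with the 8-week design and that horizon, use N=300 (or say what the 30 above 270 are for), and restate the power or the detectable difference. For 7 versus 10 weeks the power is about 58% at week 8, 80% at week 21, 85% at week 34 or 83% at study close. Restate the week-7 claim on the same basis.
3. If use after week 8 counts, say whether HR 0.70 is assumed to persist for the coaching factor once coaching ends.
4. Section 4.4.5 also lists RCT assessments at weeks 6 and 12, against weeks 4 and 8 in section 4.1.6.1. These passages must be reconciled.

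The correction to the power and endpoint text is wording only, with no extra participants or visits. If week 8 is chosen, the stated power falls or the detectable difference grows. If later use counts at a constant hazard ratio, power at N=300 stays near or above 80%.
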